2. STUDY POPULATIONS

The following analysis sets will be used:

- Safety Population (SP): all subjects who received any amount of randomized treatment.
- Full Analysis Set (FAS) (also referred to as MITT – Modified Intent-to-Treat): All randomized subjects who received at least one dose of study medication and had at least one post-baseline efficacy assessment of the primary efficacy variable.
- Per Protocol Population (PP): all subjects enrolled into the study who fulfilled all Inclusion/Exclusion criteria, did not have any major protocol violations, and completed the Initial Treatment Period of the study as planned. Completing the initial treatment period of the study as planned will include subject completion of at least 5 doses of treatment (allowing ≤ 1 missed dose, see [Section 5.2.4](#)), including the Visit 8 dose and the ICARS and CGI-C assessments performed at Visit 9 (“Month 6”) within 228 days. Subjects who discontinue the investigational product prematurely due to AEs, without protocol violations, and return for their final evaluation, will still be part of the PP population. Additional per protocol populations, including patients who complete the initial treatment period within a duration greater than 228 days, may be identified and used for sensitivity analyses.

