5.1.3 Handling Missing Data

Baseline Values

If values are missing at the baseline visit (Day 0/1), and the data are also recorded at screening, then the screening value will be used in the summaries and calculations of change from baseline. Otherwise, the baseline value will be missing for safety and efficacy endpoints.

Missing Efficacy Assessments

The missing data methods are an integral part of the data analysis for efficacy and are described in full in [Section 5.3](#). For the primary analyses of mICARS, the use of a mixed-effect model repeated measure (MMRM) model allows for missing data and assumes the data are missing completely at random (MCAR), so no imputations will be performed.

For sensitivity analysis, several multiple imputation methods will be used:

1. Impute all missing data within the original treatment group.
2. Impute all data missing due to COVID-19 related restrictions to the original treatment group and impute from the control group (Jump to Reference) for all other missing data. The COVID-19 disruption is across the entire study and can be considered as random across subject characteristics and factors that may be related to treatment or outcome, so imputation assuming Missing at Random should be appropriate. Additional factors, such as the number of treatments received, can be added to the imputation model. Details to show that these subjects continued their visits up to the point of restrictions being imposed by the pandemic and did not discontinue treatment due factors related to the study protocol or outcome will be provided.
3. Impute all missing data from the control group (Jump to Reference).

In addition, last observation carried forward [LOCF] and observed cases [OC] will be used. The LOCF method will employ the last observation carried forward; this may be the baseline value if the subject has no follow-up values. The OC method will employ only observed cases for the time points of interest (i.e., for repeated measures analysis of Visit 6 [“Month 3”] and Visit 9 [“Month 6”] both mICARS must be observed/collected to be included in the analysis). A specific analysis using retrieved dropouts will not be performed (see [Section 5.10](#)).

Missing data for all other efficacy analyses not using MMRM will use Multiple Imputation #1 as described above), with the other imputation methods, LOCF and OC, for sensitivity.

Missing Values When Computing Instrument Scores

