5.1.4 Handling Data Collected Out of Window

Efficacy scales (e.g., ICARS, QoL, etc.) collected outside of the per-protocol windows (for example, per [Appendix I](#), ICARS is scheduled for collection only at Visit 6, 9, 12, and 15) will be included in the analyses based on the nominal visit label. During the initial 6-month treatment period, Visit 9 (Month 6) must occur within 228 day window for the per protocol analysis. All data will be presented in the listings, in chronological order based on the time of collection.

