5.3.1 Primary Efficacy Variable

The modified ICARS total score from the central rater (with speech domain scores from local raters) at baseline and each follow-up visit, and the change and percent change from baseline to each follow-up visit, will be summarized using descriptive summary statistics by treatment group.

The primary efficacy variable, change from baseline to follow-up (Visit 6 [“Month 3”] and Visit 9 [“Month 6”]) in mICARS total score (described above), will be analyzed using a mixed model repeated measures (MMRM) analysis, with the baseline mICARS value as covariate and five fixed effects (treatment, age [6 to <10 years, ≥ 10 years], sex, region, visit) and one interaction term (treatment-by-visit). The treatment effect, together with the associated two-sided 95% CI and p-value will be calculated. Unstructured covariance matrices will be used. Model effect estimation will be based on restricted maximum likelihood (REML). The region-by-treatment interaction can be tested in a separate model and if a significant interaction is found, then a forest plot will be used to present the region-specific treatment effects and associated 95% confidence intervals.

The primary MMRM analysis will assume missing at random (MAR) as a means of handling missing data.

Sensitivity analyses of these primary analyses will consist of ANCOVA at Visit 9 (‘‘Month 6’’) with missing data imputed using multiple imputations as described in [Section 5.1.3](#), LOCF, and OC. The results from each of the sensitivity analyses will be compared to the primary MMRM analysis.

When applying the multiple imputation methods describe in [Section 5.1.3](#), the regression method will be used, and the imputation model will be the same as the analysis model, based on the factors treatment, sex, age (category), region, and baseline mICARS; the pattern of missing data will be essentially monotonic since none of the factors used in the model are expected to be missing. One hundred iterations of the model will be run, and the results will be combined with SAS PROC MIANALYZE. For Multiple Imputation Method #2, multiple imputation based on subjects taking the same treatment will be applied first to the missing data due to COVID-19 related restrictions, and then Jump to Reference will be applied to the remaining missing data.

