5.10 Changes to Methods Planned in the Protocol

Per protocol, sensitivity analyses are planned using three methods: LOCF, OC, and OC+RDO (observed cases plus retrieved dropouts). Each method handles missing values differently. LOCF imputes missing values by using last observation carried forward, while OC does not impute values but instead uses only observed cases. Per protocol, “Those patients who discontinue treatment prematurely but return for scheduled efficacy assessments at 6, 9 and 12 months are defined as RDOs.” According to this definition, none of these subjects would be excluded from any of the four analysis populations, and since all have efficacy assessments at three of the four ICARS time points (only missing Visit 6 [“Month 3”]), they would be included in the OC analysis (as well as all other analyses). Although RDO subjects with missing evaluations at the Visit 6 (“Month 3”) ICARS time point will not contribute a Visit 6 (“Month 3”) ICARS evaluation in the OC analysis, they will be included in the LOCF analysis. Hence, the use of the LOCF and OC methods will sufficiently incorporate the RDO subjects, and therefore the third sensitivity analysis (OC+RDO) will not be employed.

Due to deviations in the timing of the visits, the total months of treatment and assessments exceeded the 12 months as described in the protocol. The data as collected by the investigators will still be included and analyzed.

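### The imputation model leaves out the Month 3 mICARS, so MI #1 and the COVID step of MI #2 repeat the Visit 9 available-case ANCOVA

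*SAP*

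**What the plan says.** SAP 5.3.1 describes the sensitivity analyses of the primary endpoint: "Sensitivity analyses of these primary analyses will consist of ANCOVA at Visit 9", with missing values handled by multiple imputation, LOCF or observed cases (OC). Each result is to be compared with the primary MMRM. For the imputation, "the imputation model will be the same as the analysis model, based on the factors treatment, sex, age (category), region, and baseline mICARS". The reason given for using the regression method is that "the pattern of missing data will be essentially monotonic since none of the factors used in the model are expected to be missing". That reasoning suits factors known at baseline, not a post-baseline score.

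SAP 5.1.3 lists three MI methods:
- **MI #1** imputes every missing value within the patient's own arm.
- **MI #2** does this for COVID-related losses and uses Jump to Reference for the rest.
- **MI #3** uses Jump to Reference throughout.

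Under MI #2 it adds: "Additional factors, such as the number of treatments received, can be added to the imputation model".

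Two other sections show that Month 3 scores will usually be available. The FAS (SAP 2) takes only patients who "had at least one post-baseline efficacy assessment of the primary efficacy variable". SAP 5.1.4 notes that "ICARS is scheduled for collection only at Visit 6, 9, 12, and 15", so in the initial period the only scheduled post-baseline scores are Month 3 (Visit 6) and Month 6 (Visit 9).

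On OC, SAP 5.1.3 says in a parenthesis about a repeated-measures analysis that "both mICARS must be observed/collected to be included in the analysis". SAP 5.10 says of retrieved dropouts who lack only Visit 6 that "they would be included in the OC analysis (as well as all other analyses").

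**The concern.** A FAS patient with no Month 6 score must have some other post-baseline score, and in practice that is Month 3. The primary MMRM uses it. The imputation model discards it.

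This has three consequences:
- MI #1 looks like a second analysis under MAR that agrees with OC, but it is the same estimate.
- A gap between MI #1 and the MMRM may only reflect the discarded Month 3 data. It could be misread as fragility, or as extra benefit.
- Jump to Reference, in MI #3 and the non-COVID part of MI #2, is a real departure from MAR. As written, though, it also ignores how the patient was doing at Month 3. If worsening patients leave the active arm, it can lose the caution it is meant to supply.

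The same imputation methods recur in the table list for the full ICARS and the rescored mICARS.

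**Working it through.** **1. Why MI #1 equals the available-case ANCOVA.** Let b be the ANCOVA coefficients fitted to patients with an observed Month 6 score, with design matrix Xo for those patients and Xm for those missing. Imputed values average Xm·b. Refitting the same model to the completed data gives, on average over imputations,

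(Xo'Xo + Xm'Xm)^-1 (Xo'yo + Xm'Xm·b) = (Xo'Xo + Xm'Xm)^-1 (Xo'Xo + Xm'Xm) b = b.

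The imputed rows add nothing.

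**2. Numerical check.** In one simulated data set with 33 Month 6 values missing:

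| Analysis | Estimate |
|---|---|
| Available-case ANCOVA | -3.621 |
| MI #1 as written, 100 / 1,000 / 20,000 imputations | -3.569 / -3.595 / -3.622 |
| MI with Month 3 added, 20,000 imputations | -2.000 |
| Likelihood estimate using Month 3 (stand-in for the MMRM) | -2.003 |

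Over 20 scenarios of 400 trials, with 100 imputations as planned, MI #1 and available-case estimates correlated 0.9987 to 0.9996. The SD of their difference was 0.04 to 0.08.

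For the COVID step of MI #2 (20% missing, correlation 0.7): if all losses are COVID-related, MI #2 gives -3.005 against -3.009 available-case. If half are, it gives -2.639, against -2.608 when the COVID losses are simply dropped before Jump to Reference.

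**3. Inputs for size.**
- From the documents: 175 enrolled, 175/3 = about 58 per arm; effect 3.0 and SD 7.0, both within the SAP 5.1.7 ranges; 10% loss to follow-up.
- Assumed: Month 3/Month 6 correlation r = 0.3 to 0.9; log odds of missing Month 6 rising by 1.0 per SD of Month 3 worsening; 20% missing as a second level.

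The documents state no value for r. The SAP power table can be reproduced only with r = 0. For 54 per group, effect 3.0 and SD 7.0, the SD of the two-visit mean is 7 × sqrt((1+0)/2) = 4.95. Then 3/(4.95 × sqrt(2/54)) = 3.149, and 3.149 - 1.960 = 1.189 gives 88.3%, as printed. At r = 0 the omission would not matter, but repeated scores on one scale in the same patient would be expected to correlate.

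**4. One cell by hand (10% missing, r = 0.7, dropout rule in the active arm only).** Under that rule the missing patients average 0.817 SD worse than their arm at Month 3 (numerical integration). The observed patients then average -0.1 × 0.817/0.9 = -0.091 SD.
- Error in MI #1: 0.7 × 7 × (-0.091) = -0.45, so the estimate is about -3.45 against a true -3.00.
- Jump to Reference as written: 0.9 × (-3.45) + 0.1 × 0 = -3.10.
- Jump to Reference using Month 3: -3.10 + 0.1 × 0.7 × 7 × 0.817 = -2.70. This is 0.9 × (-3.00), the intended effect of removing benefit in the 10% who leave.

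A simulation of this cell gave -3.47 available-case, -3.02 with Month 3 and -3.01 with full data; Jump to Reference gave -3.12 as written and -2.72 with Month 3.

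**5. Grid (3,000 trials per cell, r = 0.3 to 0.9).** Error of MI #1 as written against full data, in mICARS points:

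| Dropout linked to Month 3 | 10% missing | 20% missing |
|---|---|---|
| Not linked (random) | none | none |
| Same rule in both arms | 0.04 to 0.09 | 0.04 to 0.18 |
| Placebo only (against the drug) | 0.24 to 0.66 | 0.40 to 1.25 |
| Active only (in its favour) | 0.20 to 0.62 | 0.39 to 1.13 |

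Conditioning on Month 3 kept the error within 0.02 in every cell.

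**6. Without bias, agreement is still lost.** With random missingness and r = 0.7, MI #1 departs from the Month 3 likelihood estimate in a single trial with SD 0.31 (10% missing) or 0.49 (20%). With Month 3 added, these fall to 0.03 and 0.05. At 20% missing the mean standard error is 1.480 as written and 1.401 with Month 3.

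**The case against.** - **The fix does not test MAR.** With Month 3 added, MI #1 mirrors the MMRM instead of OC. This stands. The gain is that MI #2 and MI #3 then condition on the same data as the primary analysis, so any movement reflects the departure from MAR.
- **The primary analysis and success rule are untouched.** Also true. SAP 5.1.10 ties success to the MMRM, which limits the point to interpretation.
- **Imputing separately by arm would break the identity.** In the single data set above it gave -3.790 against -3.621. But treatment is a listed factor, which implies one pooled model, and the by-arm version leaves the mean unchanged. At 10% missing, two checks put the SD of the difference at 0.05 and 0.11. Month 3 is still ignored.
- **The larger figures need one-sided, Month 3-driven dropout.** Fair. Only 10% loss is documented. Patients lost before any post-baseline score are outside the FAS, and Visit 9 assessments are also sought at early discontinuation, so missing Month 6 within the FAS may be below 10%. At 5% missing (an assumption) the error is about 0 for both-arm dropout and 0.10 to 0.30 for one-arm dropout, against a standard error near 1.4.
- **Extra factors may be added.** The clause is optional, sits under MI #2 and does not name Month 3.
- **The OC wording is loose rather than contradictory.** Largely accepted. The both-visits condition is written for a repeated-measures analysis, and SAP 5.10 points the other way. It still needs one definition for the Visit 9 ANCOVA.

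**Conclusion.** The concern holds. As specified, MI #1 and the COVID step of MI #2 reproduce the Visit 9 available-case ANCOVA and add no separate check of the missing-data assumption. That result is algebraic and needs no assumption about the trial.

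The size does need assumptions. Bias is nil if missingness is random, under 0.1 points if both arms follow the same rule at 10% missing, and roughly 0.2 to 0.7 points in either direction if dropout follows Month 3 in one arm only.

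For Jump to Reference, with active-only dropout and r = 0.7, the grid simulation gave -3.19 as written and -2.79 with Month 3, against -3.12 with full data (10% missing). At 20% missing the figures were -3.04, -2.34 and -2.98. As written, the analysis meant to be cautious came out slightly more favourable than full data.

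This should be corrected before unblinding, but it does not threaten the primary result.

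**What to change.** In SAP 5.3.1, add Month 3 mICARS to the imputation model for MI #1, #2 and #3:
1. Fill the few values where only Month 3 is missing with a non-monotone step (MCMC or fully conditional specification) that uses the observed Month 6 score.
2. Impute Month 6 by regression on treatment, sex, age category, region, baseline and Month 3.
3. For Jump to Reference, condition on the observed Month 3 score and state that the residual is taken from the patient's own-arm Month 3 mean.
4. Replace the sentence calling the pattern monotone, which will no longer be true by construction.

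In SAP 5.1.3, define OC for the Visit 9 ANCOVA as all patients with an observed Visit 9 score, in line with SAP 5.3.1 and 5.10. In the same edit, reconcile 5.1.3, which says the MMRM assumes MCAR, with 5.3.1, which says MAR.

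The two-step imputation was tried with a further 5% missing Month 3 only, 10% missing Month 6 and r = 0.7 (300 trials per mechanism). Bias was -0.02 with random missingness and -0.03 with placebo-only or active-only dropout, with a Monte Carlo standard error of about 0.02. In the same setting, the both-visits reading of OC would lose about 2.6 patients per arm.

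The cost is a few lines of SAP text, one more predictor and one programming step, with no new data.

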The initial double-blind, placebo-controlled treatment period will last for 6 months, with patients having a 1 in 3 chance of being randomized to placebo. After the initial 6-month treatment period, one third of the patients in the Placebo group will be randomized (1:1) to receive treatment with one of the two EDS-EP doses (Group 1: ~5-10 mg DSP/infusion; Group 2: ~14-22 mg DSP/infusion). At Month 9, one third of the placebo group will be randomly switched to EDS-EP, as above, while the remaining patients will continue to receive double-blind treatment with placebo for the remainder of the extension period. The randomization of the placebo group in a 1:1:1 fashion to be switched to EDS-EP at 6 or 9 months or remain on placebo throughout the extension treatment period will be done at baseline to avoid bias. This procedure will minimize the number of patients remaining on placebo for one year, while still providing placebo data for up to one year for comparison with EDS-EP group in the evaluation of long-term safety and efficacy. All placebo-treated patients will be eligible to start open-label treatment with EDS-EP at the one-year time-point, provided they have completed the visits at 6, 9 and 12 months (or more), meet entry criteria and provide informed consent/assent for the open-label, extension study (Study IEDAT-03-2018). In case a patient is willing to be enrolled in the open-label study IEDAT-03-2018, but the study has not yet received IRB/EC approval at the time the patient reaches Visit 15/Month 12, the patient may undergo unscheduled monthly assessments/infusions (according to the assigned blinded treatment) starting from the time Visit 15/Month 12 should be performed, and continuing until the site has been initiated for the open-label study IEDAT-03-2018 and he/she has been evaluated for eligibility for the study. This design allows all placebo-treated patients the opportunity to be treated with the active drug, while still maintaining a small number of patients on placebo for up to 12 months to facilitate collection of placebo-controlled data for analysis of long-term efficacy and safety. The optional open-label extension study will allow patients who are doing well to continue treatment with EDS as long as their physician determines they are benefitting from it and not experiencing any adverse effects that would necessitate discontinuation of treatment.

Minimization Procedure to Equalize Randomization by Gender, Age, and Region

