The randomization scheme presented in Figure 2 assumes that no patients discontinue from the study. For patients randomized to placebo at baseline, random assignments to switch to either of the active treatment groups (EDS-EP ~14-22 mg or ~5-10 mg) at Month 6 or 9, or to remain on placebo throughout the study, will be done at baseline to avoid any bias in selecting placebo patients for the switch to EDS-EP.

When the design of the pBAR randomization is in place, simulations will be used to test the randomization system. The simulations will be designed

1. to subject the pBAR implementation to conditions beyond the control of the study team, such as the order that patients arrive for randomization, to assess the robustness of the algorithm. The ability of the system to handle re-ordering of the arrival order of patients will be examined to see how well the desired balance is achieved.
2. to examine the extent to which random fluctuation will disturb the balance, both overall, and within the desired strata.
3. to subject the IVRS/IWRS system implementation to various stresses, as a validation.

Handling of Dropouts and Missing Data

Patients who discontinue treatment prematurely are defined as dropouts. Those patients who discontinue treatment prematurely but return for scheduled efficacy assessments at 6, 9 and 12 months are defined as RDOs. Missing data will be handled as described in the analysis of primary efficacy parameter. Retrieved dropouts will be used in sensitivity analyses.

Version 1.0, 09May2015; Version 2.1, 16Nov2015; Version 3.0 (Amend. 1), 01Feb2016; Version 3.1 (Amend. 2), 28Apr2016; Version 3.2 (Amend. 3), 25May2016; Version 4.0 (Amend. 4), 29Nov2016; Version 5.0 (Amend. 5, Site-specific), 20Sep2017; Version 6.0 (Amend. 6), 29Sep2017; Version 7.1 (Amend. 7.1), Final 13 March 2018, Version 8.0 (Amend. 8.0), Final 23 April 2018; Version 10.0 (Amend. 10), Final 16 April 2019; Version 11.0 (Amend. 11), Final 24 Jun 2020

Analysis of the Primary Efficacy Parameter

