5.1.8 Randomization

The milestones for the randomization process are depicted in Figure 1 and described in Items 1-4 below.

* Randomization (1:1:1; n=180, i.e. 60 per study arm) to ~5-10 or ~14-22 mg EDS or placebo using a minimization procedure for gender and age (< 10 and ≥ 10 years of age) will be done by IVRS

** All remaining placebo patients switch to ~14-22 mg EDS in study IEDAT-03-2018

NOTE: Due to the impact of COVID-19, the company decided to complete enrollment with 175 patients.

Figure 1. Trial periods and randomization/placebo switching time points.

1. **Initial Randomization.** This occurred at the start of the double-blind period. Because this trial enrolled subjects with a rare condition, the sample size was limited. Important balancing factors included gender and age (age < 10, age ≥ 10) and region. There are three treatment groups. For this situation, probabilistic baseline randomization (pBAR), or equivalently, probabilistic covariate baseline minimization was desirable. The placebo switches discussed in Items (2)-(4) were assigned at the time of the initial randomization. (See Figure 2)
2. **Switching of remaining placebo subjects after 6 months of the Initial Double-Blind treatment assignment.** Among subjects initially randomized to placebo who complete their initial 6 months of double-blind dosing, every third such placebo subject was randomized 1:1 to active dose at either the high or low dose level.
3. **Switching of remaining placebo subjects after 9 months of the Initial Double-Blind treatment assignment.** Among subjects initially randomized to placebo who complete their initial 9 months of double-blind dosing, every other such placebo subject was randomized 1:1 to active dose at either the high or low dose level.
4. **Switching of remaining placebo subjects after 12 months of the Initial Double-Blind treatment assignment.** For subjects initially randomized to placebo who complete their initial 12 months of double-blind dosing, all such placebo subjects will have been

randomized 1:1 to active dose at either the high or low dose level. These treatment assignments will be made in the open-label extension study (Study IEDAT-03-2016) for those placebo subjects who continue treatment in that study.

[figure not shown]

Figure 2. Randomization schematic

When the design of the pBAR randomization was in place, simulations were used to test the randomization system. The simulations were designed

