For the extension treatment period, the change from baseline will be the change from the last assessment prior to first infusion in the study except for the placebo subjects who switch to EDS-EP at Visits 9 and 12 (‘‘Month 6’’ and ‘‘Month 9’’, respectively). For these subjects who are switched, the baseline will be the assessment just prior to the switch. The change will be summarized for Visit 12 (‘‘Month 9’’) and Visit 15 (‘‘Month 12’’), using LOCF and OC. Because

of the small sample size and the switch from placebo to EDS-EP, no formal statistical comparisons of treatment groups will be made.

For the FAS only, the mean mICARS score will be plotted over time during the initial treatment period with separate trend lines for each of the three treatment groups. This type of plot will be repeated for mean mICARS score and mean change from baseline in mICARS score over the entire study, with separate trend lines for the seven possible dosing schemes.

For the placebo subjects who switched to EDS-EP at Visit 9 (“Month 6”), the change seen during the initial treatment period, and the change between Visit 9 (“Month 6”) and Visit 15 (“Month 12”) will be compared with a paired t-test or a non-parametric equivalent. A comparison of the change over 3 months of placebo against 3 months of treatment will also be done using the first 3 months for the subjects who switch at Visit 9 (“Month 6”) and those who switched at Visit 12 (“Month 9”).

Sensitivity Analyses

The full ICARS will be analyzed using the same methods as for the primary analysis of mICARS. The nominal p-value will be presented, and no adjustments for multiplicity will be made.

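### SAP 5.3.1 tests the effect of switching from placebo to EDS-EP on mICARS only within patients, although switch time was randomised and concurrent placebo patients exist

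*SAP*

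**What the plan says.** For placebo patients who switch at Visit 9, SAP 5.3.1 sets the change over the initial period against the change from Visit 9 to Visit 15 and states that these "will be compared with a paired t-test or a non-parametric equivalent". A second analysis follows: "A comparison of the change over 3 months of placebo against 3 months of treatment will also be done using the first 3 months", drawing on both Visit 9 and Visit 12 switchers, with no test named. On mICARS by treatment group in the extension, the section says that "no formal statistical comparisons of treatment groups will be made", and gives small numbers and the switch as its reasons.

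The switch was randomised. Protocol 7.3 describes "The randomization of the placebo group in a 1:1:1 fashion to be switched to EDS-EP at 6 or 9 months or remain on placebo" as a step taken at baseline. Protocol 16.2.8 says the assignment "will be done at baseline to avoid any bias in selecting placebo patients for the switch to EDS-EP". SAP 5.1.8 agrees: "The placebo switches discussed in Items (2)-(4) were assigned at the time of the initial randomization". At Month 6, "every third such placebo subject was randomized 1:1 to active dose at either the high or low dose level"; at Month 9, among those remaining, "every other such placebo subject was randomized 1:1 to active dose at either the high or low dose level".

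Other parts of the SAP point towards group comparisons:
- SAP 1.1 makes efficacy against placebo on mICARS the primary objective of the extension.
- SAP 3.1 says extension comparisons, mICARS included, use the methods of the initial period.
- SAP 5.1.10 repeats the comparisons at Visits 12 and 15, with p-values as a descriptive aid.
- SAP 5.3.2 fits a between-group ANCOVA to CGI-C in the extension.

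SAP 5.3.6 labels all extension efficacy analysis exploratory.

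**The concern.** The paired test compares two calendar and treatment periods in the same patients. Its null hypothesis is that mean change is equal in the two periods. That matches no drug effect only if the patients would have drifted equally in both periods without the drug.

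The documents give several reasons why they might not:
- **Non-linear progression.** Protocol 7.3 and 12.1.2 report that severity rises with age below 10 years but not above.
- **Fading placebo response.** Any early response to six months of infusions falls in the first period.
- **Selection into the extension.** Protocol 11.2 admits patients who finish the initial period and are faring well. The placebo-phase change is therefore selected, and regression to the mean can follow.
- **COVID-19.** SAP 5.1.3 describes disruption across the whole study, which need not fall equally on both periods.

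A comparison of switched with not-yet-switched patients over the same window exposes both arms to all of these. Switch time was assigned at baseline and continuation is decided under blind. Protocol 7.3 also says that the progressive, fluctuating course of the disease is why a placebo group is needed, and that some patients stay on placebo so that controlled data exist up to 12 months. The paired test uses none of those controls. At stake is how the extension's mICARS result is read: SAP section 1 expects planned analyses to go into regulatory submissions or manuscripts.

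**Working it through.** **Plan's own figure (SAP 5.2.4, Table 5, no dropout).** 60 placebo patients / 3 = 20 switch at Visit 9 (10 low, 10 high), leaving 40. Then 40 / 2 = 20 switch at Visit 12 (10 and 10), leaving 20. Table 5 reproduces exactly. With 175 randomised, 175/3 = 58.3 per arm, giving about 19 Visit 9 switchers and 39 still on placebo. The documents give no power or precision for the paired test.

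**Inputs.** The SD range of 5 to 8 and the 3.0-point difference are the planning values in SAP 5.1.7. Using that SD for a 3- or 6-month change is an assumption. The correlation rho between a patient's two successive changes and the drift difference between periods are not in the documents; both are shown over a range.

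**Standard errors.**
- Paired, 20 patients: SD × sqrt(2(1 − rho)/20)
- Randomised, 20 vs 40 (Visits 9-12): SD × sqrt(1/20 + 1/40) = 0.274 × SD
- Randomised, 20 vs 20 (Visits 9-15): SD × sqrt(1/20 + 1/20) = 0.316 × SD

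| At SD 7 | SE |
|---|---|
| Paired, rho −0.5 | 2.71 |
| Paired, rho 0 | 2.21 |
| Paired, rho +0.5 | 1.57 |
| Randomised 20 vs 40 | 1.92 |
| Randomised 20 vs 20 | 2.21 |

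The paired test beats 20 vs 40 only if 2(1 − rho)/20 < 3/40, that is rho > 0.25. It beats 20 vs 20 only if rho > 0. The two changes share the Visit 9 score with opposite signs, which pushes rho below zero; stable patient-specific slopes push it up.

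**False-positive rate of the paired test with no drug effect** (two-sided 0.05, noncentral t on 19 df, noncentrality = drift difference / SE, SD 7):

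| Drift difference (points) | rho −0.5 | rho 0 | rho +0.5 |
|---|---|---|---|
| 0 | 5.0% | 5.0% | 5.0% |
| 1 | 6.4% | 7.1% | 9.3% |
| 2 | 10.8% | 13.8% | 22.9% |
| 3 | 18.3% | 25.1% | 44.4% |

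Across SD 5-8 and rho −0.5 to +0.5, a 3-point drift difference gives 15% to 72%. Simulation (20,000 trials per setting, SD 7) agrees, and the randomised comparisons stay at about 5% whatever the drift.

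**Power of the randomised comparison for 3.0 points**, doses pooled, before dropout:

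| | SD 5 | SD 7 | SD 8 |
|---|---|---|---|
| 20 vs 40 | 58% | 34% | 27% |
| 20 vs 20 | 46% | 26% | 21% |
| One dose, 10 vs 40 | 38% | 22% | 18% |

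**The case against.** The strongest reply is that little depends on this. All extension efficacy analysis is exploratory (SAP 5.3.6), extension p-values carry no inferential weight (SAP 5.1.10), and the SAP gives a reason for avoiding group tests. The randomised contrast is also weak: well below 60% power for 3.0 points even at the smallest SD. All of this stands and limits the grade. It does not make the confounded test the better choice. The small-sample reason counts equally against a paired test on about 20 patients, and low power argues for an estimate with an interval.

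A reader might infer more than the documents support:
- **That disease progression as such biases the test.** It does not. The test sets change against change, so a constant rate cancels; only a difference in drift matters.
- **That rater learning is a major source of bias.** Central raters score videos in random order (Protocol 12.1.3) without being told the visit (Protocol 7.3). SAP section 4 leaves only the two speech items to local raters alone.
- **That the randomised comparison is always at least as precise.** This fails for rho above 0.25 (20 vs 40) or above 0 (20 vs 20, the window that matches the paired test).
- **That it uses the same patients.** It needs the placebo patients who have not switched, who are in the trial but not in the paired test.
- **That the randomised information is discarded altogether.** SAP 3.1 and 5.1.10 point to group comparisons, and SAP 5.3.1 plots all seven dosing schemes. The SAP contradicts itself here.

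**Conclusion.** The point holds as a recommended improvement to an exploratory analysis. The only test that SAP 5.3.1 names for the effect of switching on mICARS is within-patient, while a randomised concurrent control exists for the same windows. The paired test is valid only if drift without the drug is equal in the two periods. At SD 7 and rho 0, both assumed, departures of 1 to 3 points raise its false-positive rate to about 7% to 25%, against about 5% for the randomised contrast. The size of any actual drift difference is unknown. The paired test has a precision advantage only if rho is positive (20 vs 20) or above 0.25 (20 vs 40), and the documents do not give rho. Nothing here touches the primary or key secondary analysis or the trial's type I error, and a reader should not infer that it does.

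**What to change.** In SAP 5.3.1, add three exploratory ANCOVAs of change in mICARS among patients randomised to placebo:
1. Visit 9 to 12: Visit 9 switchers vs those not yet switched.
2. Visit 9 to 15: Visit 9 switchers vs never switched.
3. Visit 12 to 15: Visit 12 switchers vs never switched.

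Adjust each for mICARS at the start of the window, age, sex and region. Measure change from the start of the window in both arms: the current extension rule resets baseline for switchers only, so it would compare changes over different lengths of time. Pool the two doses for the main estimate and show each dose separately. Report estimates with 95% CIs and state the low power.

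Keep both within-patient comparisons as descriptive summaries without a test. Reconcile the exclusion of formal group comparisons in SAP 5.3.1 with SAP 3.1 and 5.1.10, so that one rule governs mICARS in the extension.

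The cost is a few lines of SAP text and a few tables. No new data are needed, and the exploratory status is unchanged.
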